12.3. Study Objectives and Hypotheses

The primary objectives of this study are (a) to determine the feasibility of giving patients and providers monthly feedback about TFV-DP levels and (b) to examine provider and patient behaviors in response to receiving this information. This trial will assess the impact of such feedback on patient and provider medication taking behaviors, and patient management (by providers) in response to receiving this information.

The study hypothesis is that participants who receive feedback on TFV-DP drug levels will have improved adherence, as assessed by monthly TFV-DP levels, VL, self-report; continuous

Wisepill use patterns, and responses to interview questions in the Exit Interviews with participants, and provider FGDs.

12.4. Randomization/Blinding Procedures/Unblinding Procedures

Participants in the pilot study will be randomized 1:1 to either Feedback Group (N=30) or No Feedback (Control) Group (N=30) by study staff using a randomization list generated by the study Biostatistician ([name]). The study will not be blinded.

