5.1.4 Aim 1 of the ADD-ART study examined the utility of using TFV-DP levels in DBS as an objective measure

of adherence to ART in South Africa. In this prospective, observational cohort study, we followed 250 HIV-positive individuals on a tenofovir-containing antiretroviral therapy and virally suppressed at study enrollment. Participants provided 12 monthly blood samples which we used to measure TFV-DP levels in red blood cells, as well as VL and other measures detailed in the Aim 1 study protocol. The study took place at the Gugulethu Research Offices (GRO) of the Desmond Tutu HIV Foundation (DTHF) in Gugulethu, 15km outside Cape Town, South Africa (SA). The study began enrolling participants in November 2017 and completed data collection in December 2019. At the time of this protocol submission, we have received the DBS-TFV-DP assay results from approximately 57% of the total study samples. Preliminary analyses of this sample supports earlier findings that TFV-DP level is strongly associated with VL measured concurrently at the same study visit, and that TFV-DP levels can predict risk of future viral breakthrough. We found that after the first signal of low drug level, participants had more than 13 times the odds of viral breakthrough (VL >400 copies/ML) two months later (when adjusting for age, sex, BMI and HCT).

5.1.5 Treatment-related feedback may motivate patients' health-promoting behaviors. Providing individuals with feedback on their performance and/or adherence to a specific treatment can influence their subsequent behaviors, leading to more health-promoting behaviors (e.g., physical activity)^{27–30}. In a study utilizing the Wisepill to assess adherence, participants found real-time monitoring acceptable³¹ and in a separate trial using PK plasma results, patients actually recommended using real-time adherence monitoring as a preferred way to promote adherence³². However, it is unknown how feedback on adherence derived from drug level assays will affect patients' ART adherence behaviors and HIV providers' clinical behavior. **Leveraging discussions from the Feedback Development Workgroups (FDWs) conducted in November 2019, we will examine the utility of giving SA patients appropriately framed feedback from the DBS TFV-DP assay in motivating them to sustain or improve adherence.**

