8.1 Inclusion/Exclusion Criteria

8.1.1. Patient Participant Inclusion Criteria

Individuals who meet all of the following criteria are eligible for inclusion in the study:

- 18 years of age or older
- HIV-positive
- Initiated ARV's containing tenofovir 4 or more months ago

- Speaks English or Xhosa
- Willing to attend 5 study visits approximately one month apart
- Willing to allow the study team to contact his/her HIV care provider about his/her monthly TFV-DP drug level
- Willing to use Wisepill to dispense ARVs for 4 months
- Willing to receive SMS and/or phone call reminders to charge the Wisepill
- Willing to allow the study team access to their medical chart/clinic folder

Participants will be recruited without regard to gender or race/ethnicity. However, based on clinic profiles, we expect the majority (about 70%) to be women and over 90% to be Black African, with the remainder, if any, of mixed race.

To generate a study sample that closely represents the clinic population, participants will be recruited regardless of VL. Based on clinic profiles, we expect the majority of participants (about 80%) to be virally suppressed based on the last standard of care (SoC) VL with the remainder being unsuppressed. The South African National Health Laboratory Service (N HLS), which assays the VL, currently uses a cut-off of less than 50 copies/mL to denote undetectable VL.

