8.4 Screening for Eligibility

After the patient gives permission to review her/his medical/research records, the study staff member will screen for eligibility by examining the medical records to confirm that the patient initiated ART containing tenofovir within the last 4 months and record the most recent VL value and date of draw.

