9.5. Clinic Chart Review (Visits 1-4 and Post Study)

Study staff will review participants' clinic charts at all visits and post-study to determine if any changes to medical or adherence management were made by providers since the previous visit. These changes could include: additional VL requests (beyond those prescribed for a stable patient), referral for intensive counsellor-based or group adherence counselling (usually only accessed if VL flagged as raised), outreach by Community Care Workers (CCWs) for adherence monitoring and support; and additional doctor-requested patient appointments. To mitigate the risk of control group participants receiving interventional DBS feedback, providers will not receive DBS results for participants in the control group.

The expected quality of the notes in the clinical charts will be variable with some clinicians making detailed notes and others making less detailed notes. The study team is reviewing FDW feedback and considering the creation of a checklist to facilitate identifying and quantifying actions that a provider may take based on DBS results .

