Because feedback begins at the first return visit at Month 1 after baseline, each Feedback Group participant will provide up to three change score outcomes (for month $i-1$ to month i for $i=2,3,4$). We will compare these to the corresponding change scores in the Control Group in a generalized linear model (GLM) using generalized estimating equations (GEE) to account for within-subject correlation (ICC) among their three change-scores. The analysis model will include a constant term and the group indicator.

With the limited pilot sample size of 60, we will be able to detect moderately large effects on average improvement in adherence. For example, if the ICC between successive change scores is no greater than 0.20, then the detectable standardized mean difference will be $2.8 * [(2/30) * (1 + 0.2 * (3-1))]^{1/2} = 0.86$, a "large" effect.

Given that this is a pilot study, our ability to explore the role of the moderating variables on adherence-related behavior will be limited. However, looking at the monthly change-scores can reveal important features on which to focus. Moreover, the larger Aim 1 sample (N=250) will provide key data on individual and structural factors affecting adherence, retention, and preferences for sample collection and feedback that we will utilize in multivariable analyses as predictors of DBS TFV-DP levels and Wisepill use patterns. We will also examine these factors as potential effect modifiers in Aim 1 analyses.

For providers we will examine changes in clinical management patterns, for example requests for additional tests or adherence counselling sessions usually only triggered by a raised VL.

Similar to Aim 1, the Baseline and Visit 4 (last visit) Quantitative Assessments will cover a large array of participant information and behaviors that could be potential confounders. To examine how potential confounding factors can influence our statistical analysis, we will first identify a list of variables that is possible be candidates for potential confounding factors and then test whether any of those variables is associated with our outcome (i.e., adherence) and exposure (i.e., the intervention) in our sample. If found, we will include them in the primary analysis model to obtain the adjusted intervention effect. While the official primary analysis will be the one without covariate adjustment, the adjusted analysis will help to interpret the findings from primary analysis.

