12.6. Participant Enrollment and Follow-Up

The study will recruit 60 HIV-positive patients who are taking ART containing tenofovir in the past 4 months. We expect to recruit an average of 15-20 participants/month for 4 months and suffer no more than 10% dropout.

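### Viral-load status is recorded before allocation and linked to the provider actions counted, yet neither the randomisation list nor the primary model uses it; it should be a prespecified covariate

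*Combined protocol and SAP*

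**What the plan says.** Allocation: section 12.4 states that participants "will be randomized 1:1 to either Feedback Group (N=30) or No Feedback (Control) Group (N=30) by study staff using a randomization list". The study biostatistician generates the list. No stratum, block size or minimisation factor is named there or elsewhere, and the trial is not blinded.

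Population: section 12.6 says "The study will recruit 60 HIV-positive patients". Under section 8.1.1, "participants will be recruited regardless of VL" and "we expect the majority of participants (about 80%) to be virally suppressed based on the last standard of care (SoC) VL". The same section gives the laboratory cut-off for undetectable VL as less than 50 copies/mL.

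Availability of VL: at screening (section 8.4), staff review the medical record and "record the most recent VL value and date of draw". Study VL samples are stored and assayed only after the participant finishes (section 9.9.1.3), so the clinic value is the one available before allocation.

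Link to outcome: objective (b) in section 6.1 names two things to examine, Wisepill adherence and clinical management. For the second, section 9.5 says that referral for intensive adherence counselling is "usually only accessed if VL flagged as raised", and section 12.1 gives as examples "requests for additional tests or adherence counselling sessions usually only triggered by a raised VL". On adherence, section 5.1.4 reports from Aim 1 that "TFV-DP level is strongly associated with VL measured concurrently at the same study visit".

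Analysis: the model in section 12.1 is a GEE on up to three month-to-month change scores, with an intercept and the arm as its only terms. Baseline and Visit 4 variables that test as associated with both outcome and arm enter an adjusted analysis, but the unadjusted one remains primary. No model is given for provider actions.

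**The concern.** By the protocol's own account, patients with a raised VL are those who usually receive the counted actions, with or without drug-level feedback. About one participant in five is expected to be in that group, and 12 people can fall unevenly between two arms of 30. If they do, the arms will differ in provider actions for a reason unrelated to feedback, and a reader of one 60-person pilot will find it hard to separate the two. Section 12.1 intends the results to supply effect estimates for a larger trial, so the precision and readability of those estimates matter. The plan holds the variable that would help and does not commit to using it.

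**Working it through.** The plan states no figure for allocation balance. Its detectable effect for the adherence analysis does reproduce: 2.8 × √[(2/30) × (1 + 0.2 × 2)] = 0.855, given as 0.86. It does not enter the calculation below.

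**Inputs.** N = 60 and 30 per arm (sections 12.4 and 12.6). Number unsuppressed K = 0.20 × 60 = 12, from the expected 80% suppressed (section 8.1.1). Action rates by VL status are not in the documents. I assume 10% in suppressed patients and a gap of 20 or 50 points.

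**1. Chance of imbalance.** With fixed arm sizes, the number X of unsuppressed participants in one arm is hypergeometric: P(X = x) = C(12, x) × C(48, 30 − x) / C(60, 30). Counting both directions:
- 8:4 or worse: 0.333
- 9:3 or worse: 0.104
- 10:2 or worse: 0.021

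Unstratified permuted blocks of 2 to 10 give the same 8:4 result (0.33 to 0.34 by simulation). Simple randomisation without fixed arm sizes gives 0.388.

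**2. Sensitivity to K.** Probability that the arms differ by 4 or more:

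| K | Probability |
|---|---|
| 10 | 0.299 |
| 11 | 0.181 |
| 12 | 0.333 |
| 13 | 0.209 |
| 14 | 0.360 |

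The zigzag is parity: with odd K the smallest qualifying difference is 5. Averaged over K ~ Binomial(60, 0.2), the probability is 0.256.

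**3. Shift in the provider-action difference.** At 8:4 the arms hold 8/30 = 26.7% and 4/30 = 13.3% unsuppressed. Shift = (8 − 4)/30 × gap:
- gap 20 points: 2.7 points
- gap 50 points: 6.7 points, or 2 patients in 30

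**4. Precision.** Standard error (SE) of the arm difference = √(2V/30). Unadjusted, V = p(1 − p) at the overall rate p. Adjusted, with VL balanced, V is the average within-group variance.
- Gap 20 (rates 10% and 30%, p = 14%): V = 0.1204, SE 9.0 points. Within groups V = 0.8 × 0.09 + 0.2 × 0.21 = 0.114, SE 8.7 points. Reduction 1 − √(0.114/0.1204) = 2.7%.
- Gap 50 (rates 10% and 60%, p = 20%): V = 0.16, SE 10.3 points. Within groups V = 0.8 × 0.09 + 0.2 × 0.24 = 0.12, SE 8.9 points. Reduction 1 − √(0.12/0.16) = 13.4%.

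So the 8:4 shift is about 0.3 SE (2.7/9.0) to 0.65 SE (6.7/10.3).

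**5. The planned confounder rule.** With 30:30 margins, the exact two-sided p-value for VL status against arm is 0.33 at 8:4 and 0.10 at 9:3. Section 12.1 gives no threshold. At an assumed 0.05, only 10:2 or worse would be flagged, which is 0.021/0.333 = 6% of the splits that are 8:4 or worse.

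**6. What stratifying would do.** With blocks of 4 or 6 within VL strata and 11 to 14 unsuppressed, the arms differ by at most 2, so the chance of a difference of 4 or more is zero.

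**The case against.** Unstratified 1:1 allocation of 60 people is valid, and chance imbalance is already reflected in the standard error. A reader might infer that the design biases the comparison; it does not, in expectation. That part of the objection stands, and the loss is in precision and interpretation only.

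The size depends on assumed action rates. Routine VL testing is annual, and chart review counts only changes since the previous visit. A raised VL from months before enrolment may have prompted its counselling before counting began. This also stands, and it makes the lower end of the range plausible.

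A reader might also infer that VL drives adherence and so distorts the Wisepill result. The documents do not support that. Section 5.1.2 has non-adherence preceding viral rebound, and month-to-month change scores remove baseline differences in level. Any remaining effect through differing room to improve is likely smaller, and it is not quantified here.

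The plan offers a partial safeguard: last VL is a baseline assessment item (section 9.7.1) and could be picked up as a confounder. But that rule usually misses an 8:4 split, feeds only a supportive analysis and is written for adherence, not provider actions.

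Finally, clinic is an equally arguable stratifier, and small blocks in an unblinded trial with staff-held allocation make assignments easier to guess. That is a fair reason not to insist on stratifying the list. It does not count against adjustment.

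**Conclusion.** The point holds as a missed, nearly free gain in precision and clarity, mainly for the provider-action half of objective (b). It is not a flaw in the validity of the randomisation.

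The one-third chance of an 8:4 or worse split applies only to exactly 12 unsuppressed. A reader might take it as the general figure, but the protocol says about 80% suppressed, so 18% to 36%, averaging about 26%, is the fairer statement. Under the assumed action rates, such a split moves the arm difference by 2.7 to 6.7 points, and adjustment would cut the standard error by about 3% to 13%. The gain is modest if screening VL predicts later actions weakly, and more useful if it predicts them strongly.

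**What to change.** In section 12.1, prespecify screening VL status (suppressed or unsuppressed at 50 copies/mL, from the last standard-of-care result recorded under section 8.4) as a covariate in the between-arm comparisons of adherence and of provider actions, whatever imbalance is observed. This adds one term to the GEE. No provider-action model exists, so one must be written; a risk difference combined across the two VL groups would be enough. State how a participant with no VL on record will be classified. Unadjusted results can be shown alongside.

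Optionally, if the list is not yet fixed, have the biostatistician stratify it by the same variable, with concealed and randomly varying block sizes.

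Cost: one extra parameter and no new data. The clinic VL may be up to about a year old, so it is an imperfect measure of status at enrolment.

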12.5. Maintenance of Trial Treatment Randomization Codes

Randomization assignment will be stored securely with all other source documents in a locked file cabinet in a locked office.

12.6. Participant Enrollment and Follow-Up

The study will recruit 60 HIV-positive patients who are taking ART containing tenofovir in the past 4 months. We expect to recruit an average of 15-20 participants/month for 4 months and suffer no more than 10% dropout.

12.7. Data and Safety Monitoring

We will work with the HIV Center's Performance and Safety Monitoring Board (PSMB) to monitor key dimensions regarding study participant recruitment, retention, and accrual of VB events.

12.7.1.1 Monitoring recruitment performance

The goal is to recruit at least 15/20 participants per month. If 10 or fewer participants are recruited for 3 consecutive months of active recruitment, the PSMB will review what recruitment problems may exist and recommend appropriate remedies. In the event that administrative or regulatory delays prevent all sites from starting recruitment concurrently, this guideline will be implemented once all recruiting sites are active.

12.7.1.2. Monitoring retention performance

For monitoring purposes, a "dropout" will be operationalized as a participant having missed two or more consecutive scheduled visits. A visit will be considered "missed" once 2 weeks have passed since the target visit date. We acknowledge that a participant who is deemed a dropout may subsequently return to the study. If at any time the percent of all enrolled participants who are current dropouts exceeds 15%, the PSMB will review and identify retention problems and recommend appropriate remedies.

12.7.2 Analysis plan.

Not applicable for this pilot trial.

13. DATA HANDLING AND RECORDKEEPING

The study will collect four distinct sources of data: (1) source documents (screening, consent, informed consent, and participant contact information); (2) assessment data; (3) blood specimen data; and (4) Wisepill data. Study participants will be identified using a confidential PID.

Data from source 1 (source documents) will contain identifiable data and will be stored separately from all other data sources, which will only contain de-identified data. Consent forms from source 1 will be stored in a locked file cabinet in a locked office, and the locator form (which contains the link between patients and their unique PIDs) will be stored in a password protected file on a shared DTHF drive folder on an encrypted study computer stored in a locked office.

All other data will be labeled only with the PID and will not contain any identifiable information. All data from source 2 (assessment data) will be collected electronically on password protected and encrypted tablets. Data on the tablets will be electronically transmitted to a secure, remote and HIPAA compliant server with partitioned and dedicated space for this study only, known as the 'study server'. Only authorized users will be able to log into the server to view and download data for analysis. The server will maintain an audit trail of all log-ins, edits, and log-outs. Data collected on the tablets can be recorded with or without an internet connection. When there is a connection, the data will be automatically uploaded to the secure study server that will require password authentication. When there is not an internet connection, the data will be cached on the tablet and automatically upload once an internet connection is established. The data will be automatically deleted from the tablet once the upload to the study server is complete and the server will send an automatic email to the US SCO indicating that new data have been uploaded. Access to the data collected on the tablets and stored on the study server will be limited to only those study personnel with data access rights. The US SCO will monitor the study server to ensure that the data collected and uploaded to the server are complete and to monitor for suspicious data activity.

Data from source 3 (blood specimens) will be documented as follows and will be identified only by the unique PID. Hematocrit results will be entered into the tablet at the time of the study visit (when the sample is processed). VL results for each patient will be processed once the patient has completed the study and will be accessible via a secure web portal managed by the NHLS. The study staff will enter these data into a study database located on the study server. DBS results processed at the UCT Clinical Pharmacology laboratory and will be entered into a database on the study server.

Data from source 4 (Wisepill data) will be stored on a separate, remote, password protected secure server.

Local IRB/Ethics Committees, Site Monitors, the NIAID, the OHRP, and other local or international regulatory authorities/entities may review study records.

13.1. Source Documents

Source documents, including screening and enrollment logs, informed consents forms, and permission forms relating to social impact events will be stored securely in a locked file cabinet in a locked office.

13.2. Assessment Data

Study staff will collect the following assessments from study participants using a secure, encrypted, password-protected tablet: (1) Baseline Assessment; (2) Self-Reported Adherence

Questionnaire; (4) Pregnancy Status, and (5) Final Assessment. To minimize data entry errors and missing data, the data collection program installed on the tablet will be programmed with automatic skip patterns, requirements that each item be answered or refused, and acceptance of only values within the appropriate range of responses for that item. To ensure that the correct assessment and procedures are completed at each study visit, the data collection program installed on the tablet will be programmed to include only the study assessments and procedures relevant to that visit. All data collected on the tablet will be time- and date-stamped, and uploaded to the study server.

13.3 Blood Speciment Data

Study staff will record the collection of specimens from the participant using a secure, encrypted, password-protected tablet for the following assessments: (1) DBS; (2) VL specimen; and (3) hematocrit test. To ensure that the correct specimens are collected at each study visit, the data collection program installed on the tablet will be programmed to only include the specimen collection procedures relevant to that visit.

Study staff will identify the specimens using scannable barcodes, which will contain information on the participant ID numbers, the type of specimen, and the visit number. Study staff will store specimens according to the Blood Specimen Storage SOP.

13.3.1. Specimen transport, analysis and long-term storage.

Study staff will deliver the VL cryovials from the freezer located at the GRO to J52 Groote Schuur CRS for storage and later to the NHLS located at the Groote Schuur Hospital campus for analysis at the end of the study. Study staff will scan the barcodes for each VL tube delivered to the NHLS using the camera function on the tablet to document which vials are being transported. Once at the NHLS, the Lab Assistant will sign the tablet to indicate that s/he has received the VL vials.

VL results will be processed by the NHLS and will be accessible via a secure web portal managed by the NHLS. Study staff will enter these data into a study database located on the study server. Once entered, the study server will automatically send an email to the US SCO indicating that test results are available.

